**Study RWE-003**

Title	Real-World Evidence (RWE) of Usage of Nerivio, a Remote Electrical Neurostimulation (REN) Device In Adolescents Patients With Migraine
Sponsor	Theranica Bio-Electronics Ltd. [name]
Investigational Device	
Nerivio is a Remote Electrical Neuromodulation (REN) wearable, battery-powered medical device for the acute and/or preventive treatment of migraine with or without aura in patients 12 years of age or older. Nerivio is controlled by a mobile application. Nerivio is intended for self-administration in a home healthcare environment.
 
The device is worn on the upper arm and transmits transcutaneous remote electrical nerve stimulation by applying weak electrical pulses that invoke conditioned pain modulation (CPM) to inhibit migraine pain. Nerivio is intended for self-administration at the onset of a migraine episode.

Objectives	To evaluate the safety, utilization and efficacy of Nerivio in adolescent patients (Age 12-18) who used the Nerivio device for treating their migraine
Patient Population	Nerivio users aged 12-18 years old who registered a Nerivio account and used the Nerivio device for the acute treatment of migraine.
Sample size	The sample size will includes all Nerivio users in the age of 12-18 in the Nerivio database who treated with Nerivio at least once between Jan 01, 2021 and May 31, 2022
Inclusion criteria	

• Age between 12-18 years

• REN user across the United States who created Nerivio account on January 1st, 2021 until May 31, 2022.

• Had at least two evaluable treatments with the Nerivio device (for consistent efficacy analysis).

Exclusion criteria	

• Treatments shorter than 20 minutes will not be included in the analysis

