Study Design	
The analysis included patients at the age of 12-18 (at the day of opening a Nerivio account) with migraine across the USA who used Nerivio at least once between January 01, 2021, and May 31, 2022.
 
Treatment data will be collected through the Nerivio app (Nerivio®) which is required for treatment. Device output current is set by the user to be strong but not painful and is equivalent to treatment dosage (max device current 40 mA on 0-100 units user-facing scale). Additionally, patients can voluntarily log details about their symptoms at both treatment onset and 2-hours post-treatment status. Treatment efficacy will be measured by consistent reduction in headache pain intensity and functional disability at 2-hours post-treatment, based on data from patients who voluntarily will answer the pre and post treatment questionnaires. Safety will be assessed by the rate of device related adverse event reported by the patients.

Evaluable Treatment	
Evaluable treatment is a treatment that meets all the following criteria:
 

• Baseline and 2-hour post-treatment pain intensity and functional disability scores were recorded.

• The participant did not use any concomitant acute migraine medication during the treatment.

Efficacy endpoints	

1. Pain Relief: Reduction in pain intensity from moderate or severe (baseline score of 2 or 3) to mild or no pain (score of 1 or 0) at 2 hours post-treatment.

2. Pain Freedom: Reduction in pain intensity from mild, moderate, or severe (baseline score of 1, 2, or 3) to no pain (score of 0) at 2 hours post-treatment.

3. Functional Disability Relief: Reduction in functional disability by at least one point from baseline at 2 hours post-treatment.

4. Functional Disability Freedom: Reduction in functional disability from mild, moderate, or severe (baseline score of 1, 2, or 3) to no disability (score of 0) at 2 hours post-treatment.

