Utilization endpoints	

5. Consistent Usage of Migraine Abortive (Rescue) Medications: The proportion of subjects with REN treatments without the use of pharmacological migraine abortive (rescue) medication (either over the counter or prescribed), or with a combination of rescue medication or without any treatment at all at 2 hours post-treatment in at least 50% of all their treatments.

6. Treatment intensity distribution: The mean intensity of the stimulation collected for all treatments that were performed within the study

Safety endpoints	Rate of serious adverse events, adverse events and device-related adverse events

Data collection	
Data will be collected prospectively through the Nerivio smartphone application. At the time of creating a Nerivio account on the App, patients (and their parents, in case of patients younger than 18) are required to sign a consent statement presented to them, where they agree that their deidentified data may be collected and used for reserve purposes.
 
Prospective data was collected for Nerivio users in the United States who treated their migraine attacks with the Nerivio device. Nerivio utilization, and Nerivio treatment reports at T=0h and T=2h were extracted from the Nerivio server in an unidentified manner. Data will be analyzed per user following additional analysis per the target population.
 
The following data will be extracted:
 

• Demographics: Age at registration, gender.

• Treatment Details: Treatment date, baseline pain intensity, pain intensity at 2 hours post-treatment, baseline functional disability, functional disability at 2 hours post-treatment.

• Treatment Frequency: Number of treatments per month over the 12-months period.

• Pain Intensity: 0 (no pain), 1 (mild), 2 (moderate), 3 (severe).

• Functional Disability: 0 (no disability), 1 (mild interference), 2 (moderate interference), 3 (severe interference).

• Additional migraine symptoms (Nausea/ vomiting, Photophobia, Phonophobia)

Statistical considerations	See at the end of the document
Responder Definition	For each efficacy endpoint, a participants will be considered a responder if they achieved the defined outcome in at least 50% of their evaluable treatments during that study period.

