### **Utilization Endpoints Analysis**

Utilization outcome will be calculated from the treatment parameters (intensity levels) and the treatment reports (usage of rescue medications), and will be presented in appropriate distribution tables.

Qualifies treatment was defined as

1 - Attacks treated with Nerivio for at least 20 minutes

2 - Pre and post treatment data were reported by the participant for the specific treatment

3 – No rescue medications were taken before and during the 2 hours post treatment, according to the participant report

Consistent efficacy will be conducted in cases where at least two qualified treatments were performed. Patients who experienced the outcome (e.g., pain freedom) in at least 50% of their reported treatments, during which they did not report the use of rescue medications, were considered responders.

Headache pain and functional disability will be rated at baseline and at 2 h post-treatment on a 4-point scale: severe, moderate, mild, or none. Migraine associated symptoms (photophobia, phonophobia, and nausea/vomiting) will be marked as present or not.

Pain relief will be calculated as a decrease from severe or moderate levels at baseline to mild or none at 2 h posttreatment.

Functional disability relief will be calculated as any improvement in disability from baseline to 2 h posttreatment.

Pain/functional disability freedom will be calculated as a decrease from any pain/disability level at baseline to none at 2 h post-treatment.

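### Endpoint 5 applies its 50% rule to all treatments, but rescue-medication status is known only for treatments that the user reported

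*Combined protocol and SAP*

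**What the plan says.** Item 5 under Utilization endpoints asks for the proportion of subjects who used REN without rescue medication, or together with it, "in at least 50% of all their treatments". A third alternative follows, "or without any treatment at all at 2 hours post-treatment", which is not defined anywhere. Item 6, next to it, also refers to every treatment performed in the study.

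On data sources, the Utilization Endpoints Analysis section takes medication use from "the treatment reports (usage of rescue medications"), and its definition of a qualified treatment makes medication status depend on what the participant reported. The Treatment Data section separates automatic parameters (time, location, serial number and intensity are its examples) from information that the participant completes; medication is not among those examples. Under Study Design, "patients can voluntarily log details about their symptoms at both treatment onset and 2-hours post-treatment status", and the pre- and post-treatment questionnaires are also described as voluntary.

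The efficacy rules use narrower denominators: "at least 50% of their evaluable treatments" under Responder Definition, and "in at least 50% of their reported treatments, during which they did not report the use of rescue medications" in the Utilization Endpoints Analysis section. One restriction applies throughout: "Treatments shorter than 20 minutes will not be included in the analysis".

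**The concern.** The denominator in endpoint 5 is wider than the data that feed its numerator. A 30-minute treatment with no report passes the duration filter and is one of the user's treatments, yet nobody knows whether medication was taken. Under the literal rule it cannot count towards either the with-medication or the without-medication group, but it still counts in the 50% threshold for both. A user who reports rarely can then fail both thresholds however medication was actually used.

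The stated objective is "To evaluate the safety, utilization and efficacy of Nerivio in adolescent patients", and endpoint 5 is the only endpoint on medication use alongside the device. If reporting is incomplete, a low figure in the without-medication row could be taken for heavy medication use when it shows only missing reports. No hypothesis test, efficacy result or safety result depends on it.

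**Working it through.** The plan gives no expected value for endpoint 5, so there is no figure to reproduce. The size can only be illustrated.

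**Assumptions, none from the documents.** Each user has n = 5 treatments of at least 20 minutes. Each treatment is medication-free with probability p and reported with probability r, and reporting is independent of medication use. Let a be the number reported medication-free, b the number reported with medication, and 5 − a − b the number unreported.

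**Literal rule.** A user enters the without-medication row if a ≥ 2.5, so the share is P(Binomial(5, rp) ≥ 3). For the with-medication row it is P(Binomial(5, r(1−p)) ≥ 3).

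**Reported-only rule.** A user enters the without-medication row if a ≥ (a+b)/2, given at least one report.

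**p = 0.6, r = 0.5, literal.**
- Without medication, rp = 0.3: 0.1323 + 0.0284 + 0.0024 = 0.163.
- With medication, r(1−p) = 0.2: 0.0512 + 0.0064 + 0.0003 = 0.058.
- In neither row: 1 − 0.163 − 0.058 = 0.779.

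**p = 0.6, r = 0.5, reported only.** The chances of 1, 2, 3, 4 or 5 reports are 5, 10, 10, 5 and 1 in 32. Given that many reports, the chances of at least half being medication-free are 0.600, 0.840, 0.648, 0.821 and 0.683. The weighted result is (3.000 + 8.400 + 6.480 + 4.104 + 0.683)/31 = 22.667/31 = 0.731.

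**p = 0.6, r = 0.9, literal.** rp = 0.54: 0.333 + 0.196 + 0.046 = 0.575 (0.5747 unrounded). Reported only gives 0.727.

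Share of users in the without-medication row, literal / reported only:

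| Report rate | p = 0.6 | p = 0.4 |
|---|---|---|
| 30% | 4% / 70% | 1% / 49% |
| 50% | 16% / 73% | 6% / 48% |
| 70% | 35% / 74% | 14% / 45% |
| 90% | 57% / 73% | 25% / 39% |
| 100% | 68% / 68% | 32% / 32% |

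With 10 treatments per user, p = 0.6 and r = 0.5, the pair is 15% and 75%, so the gap does not come from choosing five treatments.

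**Ties.** A threshold of at least 50% admits an exactly split user to both rows. At p = 0.6 and r = 0.5, ties need 2 or 4 reports: (10 × 0.480 + 5 × 0.346)/31 = 6.528/31 = 0.21 of users with a report.

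**Users with fewer than two reports.** (1−r)^5 + 5r(1−r)^4 is 0.168 + 0.360 = 0.53 at r = 0.3, 0.031 + 0.156 = 0.19 at r = 0.5, 0.002 + 0.028 = 0.03 at r = 0.7, and below 0.001 at r = 0.9.

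**The case against.** The best reply is that the plan already answers the question. The Utilization Endpoints Analysis section says that this outcome is calculated from the reports, and a treatment without a report supplies no medication datum. On that view, the word all only contrasts with the evaluable subset used for efficacy. Endpoint 5 could not use that subset, because it excludes the medication use being counted. Much of this stands: reported treatments are the likely intent, and the contrast with evaluable treatments is weak evidence of an error. But the endpoint's own words still set a different denominator, item 6 beside it uses a similarly unrestricted one, and no sentence says how an unreported treatment counts.

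It is also fair that voluntary reporting of medication is an inference. The sentence under Study Design concerns symptoms, and the list of automatic parameters gives examples only. The inference is reasonable given the voluntary questionnaires and the reliance on participant reports, but it is not stated.

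The inclusion criterion of two evaluable treatments might seem to remove the problem. Its parenthesis ties it to the consistent-efficacy analysis, and it does not make a user's other treatments reported. If it did govern the whole cohort, no user would be lost under a two-report minimum, but the gap would remain. At p = 0.6 and r = 0.5, conditioning on a ≥ 2 gives 0.163/0.472 = 35% for the literal rule and (0.472 − 0.007)/0.472 = 98% for reported only.

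A reader might go further and infer that unreported treatments would count as medication-free, giving 94% at p = 0.6 and r = 0.5. The documents do not support this. The only wording that could suggest it, "in at least 50% of their reported treatments, during which they did not report the use of rescue medications", is an efficacy rule that already limits itself to reported treatments.

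**Conclusion.** The point holds as a minor defect of wording. As written, endpoint 5's 50% rule covers treatments whose medication status is unknown, which lowers both rows whenever reporting is incomplete. Under the assumed inputs (5 treatments, 60% medication-free share, reporting independent of medication use), the without-medication row is 16% against 73% at 50% reporting and 57% against 73% at 90%. The gap closes at full reporting. The actual size is unknown, because the documents give no treatment counts, report rates or medication rates.

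A reader might infer that the choice of denominator always moves the result across one half. It does not: at a 60% share both figures are above half at 90% reporting, and at a 40% share both stay below half at every rate shown. Nor does the efficacy evidence depend on this endpoint. The phrase "or without any treatment at all at 2 hours post-treatment" is undefined and sits oddly where every unit counted is a REN treatment, but that alone is a drafting matter.

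**What to change.** Reword endpoint 5 as follows:

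- The denominator is the user's treatments of at least 20 minutes with reported medication status.
- Include users with at least two such treatments, in line with the plan's two-treatment minimum for consistent efficacy.
- Report REN without medication and REN with medication as separate, mutually exclusive rows, with a stated tie rule, for example a third row for users split exactly 50/50.
- Give the number of treatments, and of users, without reported status, and do not count a missing report as no medication.
- Delete the undefined third alternative.

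This needs no new data: a wording change, a row for ties and two counts. The cost is that users with fewer than two reported treatments leave this endpoint: in the illustration 19% at 50% reporting and 53% at 30%, but under 0.1% at 90%.

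The tie row also changes the figure. At p = 0.6 and r = 0.5, users with at least two reports divide into 13.139/26 = 51% without medication, 6.528/26 = 25% tied and the remaining 24% with medication.

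The result will still depend on who chooses to report. With few reports per user it can also differ from what full reporting would show; in the example with p = 0.4 and r = 0.5, the reported-only share before ties are separated is 48% against 32%. That is why the unreported counts should stand beside the rows.

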## **STATISTICAL CONSIDERATIONS FOR RWE-003 STUDY**

The study hypothesis was that treatments of migraine with the Nerivio device In adolescents will demonstrate similar results to the results previously found in adults

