### **Efficacy Endpoints Analysis**

Generalized linear mixed model (GLMM) will be used to compare the effect of treatment month on efficacy rate outcomes.

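### The responder rule, as written, sets no baseline-score condition on its denominator, so treatments that could not show the outcome count as failures

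*Combined protocol and SAP*

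**What the plan says.** The synopsis (Study RWE-003, Responder Definition) applies one rule to each efficacy endpoint: a participant responds "if they achieved the defined outcome in at least 50% of their evaluable treatments during that study period". Under Evaluable Treatment, the requirement on scores is only that "Baseline and 2-hour post-treatment pain intensity and functional disability scores were recorded"; the other condition is that no concomitant acute migraine medication was used.

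The statistical section (Utilization Endpoints Analysis) restates the rule for patients with the outcome "in at least 50% of their reported treatments, during which they did not report the use of rescue medications, were considered responders". Its definition of a qualified treatment covers duration, absence of rescue medication, and data: "Pre and post treatment data were reported by the participant for the specific treatment". The minimum is also set without reference to baseline: "Consistent efficacy will be conducted in cases where at least two qualified treatments were performed".

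Baseline scores appear only inside the outcome definitions (synopsis, Efficacy endpoints). Pain relief starts from 2 or 3. Pain freedom and disability freedom start from 1, 2 or 3. Disability relief is a drop of at least one point with no starting level named, and the statistical section says the same: "Functional disability relief will be calculated as any improvement in disability from baseline to 2 h posttreatment".

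Under Efficacy Endpoints Analysis the month comparison is one sentence: "Generalized linear mixed model (GLMM) will be used to compare the effect of treatment month on efficacy rate outcomes". It does not say which treatments form the rate. The study hypothesis is that adolescents "will demonstrate similar results to the results previously found in adults".

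**The concern.** Both scales run from 0 to 3 (synopsis, Data collection), so a baseline pain of 0 or 1, or a baseline disability of 0, can be recorded. Such a treatment meets the evaluable definition and enters the denominator, but for the endpoints concerned it can never enter the numerator.

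The responder rate then reflects how severe attacks were when treated as well as what happened after treatment. A user who often treats early, while pain is still mild, is penalised on pain relief for doing so. The hypothesis is similarity to adult results, so a rate that moves with baseline mix, or that is built on a different denominator from the adult figure, weakens the comparison. The same applies across months if baseline severity changes over time. Two competent analysts could also report different responder rates from the same data and each defend the choice from the text.

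**Working it through.** The plan states no expected rate, sample size or success threshold, so there is no figure of its own to reproduce.

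**1. Which baselines make the outcome impossible** (synopsis definitions and scales)

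| Endpoint | Baseline range in the definition | Baselines that cannot succeed |
|---|---|---|
| Pain relief | 2-3 | 0, 1 |
| Pain freedom | 1-3 | 0 |
| Disability relief | none stated | 0 |
| Disability freedom | 1-3 | 0 |

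**2. The two rules for one user.** Let N be evaluable treatments, E those with an eligible baseline (E ≤ N), and S successes.

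- Literal rule: S ≥ 0.5N, so at least ceil(0.5N) successes.
- Eligible-only rule: S ≥ 0.5E, so at least ceil(0.5E) successes.

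Because E ≤ N, any user with E ≥ 1 who passes the literal rule also passes the eligible-only rule. For a fixed set of users the literal rule can therefore only lower the rate.

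| N | E | Literal needs | Eligible-only needs |
|---|---|---|---|
| 5 | 4 | 3 | 2 |
| 5 | 2 | 3 (impossible) | 1 |
| 10 | 8 | 5 | 4 |
| 4 | 3 | 2 | 2 |
| 10 | 9 | 5 | 5 |

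The last two rows show a general result: when N is even and exactly one treatment is ineligible, the rules agree.

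Examples for pain relief:

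- Baseline pain 1, 1, 1, 2, 2 with both eligible treatments relieved: 2/5 = 40%, non-responder, against 2/2 = 100%, responder.
- Baseline pain 1, 2, 2, 2, 2 with two of the four eligible treatments relieved: 2/5 = 40%, non-responder, against 2/4 = 50%, responder.

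A user with fewer than half of treatments eligible can never respond under the literal rule.

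**3. Size across users (illustration; every input is assumed).** One million simulated users per setting; N uniform on 2-10; each user's success probability Beta with mean 0.6 and concentration 3; each user's eligible share Beta with mean q and concentration 4; the two independent. Both rules are applied to the same users, those with E ≥ 2.

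| Mean eligible share q | Literal | Eligible-only | Gap (points) | Users with E < 2 |
|---|---|---|---|---|
| 99% | 67.7% | 68.3% | 0.6 | 0.3% |
| 95% | 65.4% | 68.3% | 2.9 | 1.6% |
| 90% | 62.3% | 68.3% | 6.0 | 3.3% |
| 80% | 56.1% | 68.7% | 12.6 | 7.6% |
| 70% | 49.4% | 68.9% | 19.5 | 13.2% |

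The inputs were then varied one at a time: mean success 0.4-0.7, success concentration 1.5-10, eligible-share concentration 2-20, and the range of N from 2-4 to 2-20. The same-user gap ran 1.5-3.8, 3.0-7.7, 6.0-15.5 and 8.9-23.7 points at 95, 90, 80 and 70% eligible. Independence of eligible share and success was kept throughout.

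**4. Month comparison.** If the rate is per treatment over all evaluable treatments, it equals e × p, where e is the eligible share and p the success probability on eligible treatments. With p fixed at an assumed 0.60 and e falling from 0.90 to 0.80 between months, the rate goes from 0.90 × 0.60 = 54% to 0.80 × 0.60 = 48%, although the effect has not changed. The marginal odds ratio is (0.48/0.52)/(0.54/0.46) = 0.79. A mixed model estimates a conditional odds ratio, so this shows the direction of the artefact and is not a prediction of the model's output.

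**The case against.** The strongest reply is that this is an ambiguity. Three of the four endpoints carry a baseline range, and the statistical section repeats those ranges in words. They can naturally be read as saying which treatments the endpoint applies to. For disability relief, a one-point drop on a 0-3 scale implies a start of 1-3. This stands in part: the ranges may well be meant that way. But they are written as part of what counts as success, the denominator is stated separately as evaluable or reported treatments, and no sentence removes the rest. For disability relief no range is given at all.

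A second reply is that the literal rule is conservative, because it cannot flatter the device on a fixed set of users. That is true. It is less reassuring when the hypothesis is similarity to an external result: a downward shift that depends on case mix is not automatically safe there.

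A third reply concerns size. A reader might reason that, with eligible share e, a user must succeed in 0.5/e of eligible treatments (56% at 90%), and take the excess over 50% as the penalty. That overstates it, because the eligible-only rule also rounds up: with 9 eligible of 10, both rules need 5. A reader might also set the literal rate on all users (45% at 70% eligible) against the eligible-only rate on users with at least two eligible treatments (69%). That mixes a change of rule with a change of users; on the same users it is about 49% against 69%.

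**Conclusion.** The point holds as a defect in the stated rule. Followed as written, it counts as failures treatments that could not have shown the outcome. This concerns mainly pain relief (baseline 0-1) and the two disability endpoints (baseline 0). Pain freedom is touched only by baseline pain 0, probably rare, and the illustrated difference is under 1 point at 99% eligible.

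The direction, for a fixed set of users, is certain. The size is not: it depends on a baseline mix that the documents do not give. The gaps of about 3, 6, 13 and 20 points at 95, 90, 80 and 70% eligible rest on assumed inputs, including independence between eligible share and success.

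Two stronger inferences are not supported. One is that the analysis will in fact score these treatments as failures: an analyst might apply the ranges as eligibility conditions. The other is that a conclusion changes: the plan sets no success threshold, margin or reference rate, so no decision is shown to reverse. Distortion of the adult or month comparison is likewise conditional, on the unstated adult denominator and on whether baseline mix differs. The point should be fixed, because the correction is cheap and the reported rate may depend materially on it.

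**What to change.** In the Responder Definition and in Utilization Endpoints Analysis, define each endpoint's denominator as evaluable treatments with an eligible baseline:

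- pain relief: baseline pain 2-3;
- pain freedom: baseline pain 1-3;
- disability relief and disability freedom: baseline disability 1-3.

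Use one term for these treatments in place of evaluable, qualified and reported. Use the same treatments in the month comparison under Efficacy Endpoints Analysis and state whether its unit is the treatment or the user. Report the all-evaluable version as a sensitivity analysis, both on all users and on the same users as the main analysis. Give the denominator behind the adult results used for comparison.

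State how users with fewer than two eligible treatments for an endpoint are handled. Applying the two-treatment minimum separately to each endpoint is one option, with the number of users lost reported; a user with baseline pain 1, 1, 1, 2 would then drop out of pain relief and would not become a responder.

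The cost is about one sentence per endpoint, one for the mixed model and one extra table; the baseline scores are already extracted. The downside is that user sets may differ by endpoint, and some users will have few or no eligible treatments. Under the per-endpoint minimum, the illustration loses about 2/3/8/13% of users at 95/90/80/70% eligible, and up to 29% at 70% if users have only 2-4 treatments. Because the users then change as well as the rule, the group rate could move either way.
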